10.7.4 COVID-19 Case Definition for Primary Efficacy Analysis

A case of COVID-19 meeting the case definition for primary efficacy analysis is defined as follows:

- Virologically-confirmed case of COVID-19 (of any severity) defined as a positive SARS-CoV-2 specific RT-PCR test in a person with clinically symptomatic COVID 19, see Section 10.7.2.
- Symptom onset \geq 15 days after second trial vaccination, i.e.

Start date of symptoms – date of second vaccination \geq 15 days.

See Section 10.7.2 for further details on definition of symptom onset.

- First episode of virologically-confirmed COVID-19, i.e. the subject must not have a history of virologically-confirmed COVID-19 illness at enrollment or have developed a case of virologically-confirmed COVID-19 before 15 days after the second trial vaccination.
- Subject is SARS-CoV-2 naïve at baseline and Day 43 (defined as seronegative to N protein in the blood samples collected at baseline and Day 43). See Section 10.6.1 for further details.

10.7.5 SARS-CoV-2 Genome Lineage Characterization

The characterization of SARS-CoV-2 variants are implemented as per Protocol Section 9.2.1.6. The following phylogenetic clustering is applied:

1. “Wild type” virus
2. “Alpha” variant of concern (VOC)
3. All other VOCs.

In this trial, the primary efficacy endpoint is based on all strains, the “wild type” virus and all SARS-CoV-2 variants (as defined under numbers 1, 2 and 3 above); the key secondary efficacy endpoint is based on the “wild type” virus and the Alpha variant (as defined under numbers 1 and 2 above); and the exploratory efficacy endpoint is based on disease caused by individual VOCs (as defined under numbers 2 and 3 above).

Genome lineage characterization of the SARS-CoV-2 viruses has been requested to stop on 01-Sep-2021.

10.7.6 Adjudication of COVID-19 Cases

An independent Committee of clinicians is formed to adjudicate all COVID-19 cases, and asymptomatic cases of SARS-CoV-2 infections (Section 10.8). The Committee is blinded to the treatment assignments of the subjects. The cases are adjudicated by the members with respect to the following questions:

- Is the case a virologically-confirmed case of COVID-19 defined as a positive SARS-CoV-2 specific RT-PCR test in a person with clinically symptomatic COVID-19 with one or more of the symptoms listed in Section 10.7.1?
- Was the RT-PCR test performed at the CureVac designated central laboratory?
- Was the symptom onset of the case \geq 15 days following the second vaccination? Or did it occur before 15 days following the second trial vaccination?
- Was the subject naïve or non-naïve to SARS-CoV-2 at baseline and Day 43? (defined as being seronegative or seropositive to the SARS-CoV-2 N protein at baseline and Day 43).
- Was the subject 18 to 60 years of age or \geq 61 years of age?
- Was the subject asymptomatic? If asymptomatic, was the RT-PCR test positive \geq 15 days following the second vaccination or before?
- Was it a mild, moderate or severe case of COVID-19 based on the provided clinical definitions?
- Did the subject require supplemental oxygenation? What type of oxygen support did the subject receive?
- Was the subject hospitalized? Was the subject admitted to the ICU?
- Did the subject die? Due to COVID-19 or another cause?

COVID-19 case summary data as provided by the Adjudication Committee is used for all relevant definitions and analyses, i.e. especially all primary efficacy cases have to be confirmed by the Adjudication Committee. Where the adjudicated data conflicts with other data recorded on the CRF (e.g. severity of the event, or

baseline serology status), the adjudication data generally overrules the other data available. This applies to both COVID-19 cases and asymptomatic cases of SARS-CoV-2 infections.

Exceptions:

1. For the analysis of COVID-19 cases by age group, the age at trial entry as recorded on the CRF rather than the age at onset (as assessed by the Adjudication Committee) is used.
2. The case onset date is also taken from the CRF, irrespective of the onset date recorded on the Adjudication Form.

COVID-19 case adjudication stopped on 18-Jun-2021 (cut-off date for the final efficacy analysis) and is not to be re-started again, also not in a possible open-label phase. The determining factor for the adjudication cut-off was the central PCR test date.

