
 Occurrence of first episodes of virologically-confirmed (RT-PCR positive) cases of "wild type" and "Alpha" SARS CoV 2 strains in SARS CoV 2 naïve subjects. 	
In naïve evaluable subjects (complying with the definition of Efficacy Analysis Set) at least 15 days following second vaccination:
 
$VE = 1 - RR$ with exact 95% CI

Other Secondary Efficacy	

 In subjects ≥ 61 years of age, occurrence of first episodes of virologically-confirmed (RT-PCR positive) cases of COVID-19 of any severity meeting the case definition for the primary efficacy analysis. 	
In naïve evaluable subjects ≥ 61 years of age at randomization (complying with the definition of Efficacy Analysis Set) at least 15 days following second vaccination:
 
$VE = 1 - RR$ with exact 95% CI

 BoD scores calculated based on first episodes of virologically-confirmed (RT-PCR positive) cases of COVID-19 of any severity 	
Where RR is the ratio of attack rates of COVID-19 cases per 100 person-month in the CVnCoV vaccine group over the placebo group
 
In naïve evaluable subjects (complying with the definition of Efficacy Analysis Set) at least 15 days following second trial vaccination:

ENDPOINTS (subject level)	ESTIMANDS (population level)

meeting the case definition for the primary efficacy analysis.
 
 ○ BoD #1 – no disease (not infected or asymptomatic infection) = 0; mild or moderate disease = 1; severe disease = 2. ○ BoD #2 – no disease (not infected or asymptomatic infection) = 0; disease without hospitalization = 1; disease with hospitalization = 2; death = 3. 	$VE_{BOD} = 1 - SV/SP$ with exact 95% CI 
Where SV denotes the ratio of mean BoD score in the CVnCoV group and the mean follow-up time (years) in the CVnCoV group and SP denotes the ratio of mean BoD score in the placebo group and the mean follow-up time (years) in the placebo group.

 ● Occurrence of first episodes of virologically-confirmed (RT-PCR positive) cases of COVID-19 of any severity with symptom onset at any time after the first trial vaccination. 	
In naïve subjects who received at least one dose of CVnCoV or placebo vaccine at any time after the first vaccination:
 $VE = 1 - RR$ with exact 95% CI
Secondary Immunogenicity	

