10.14 Age Group

Subjects are assigned to age groups “18 to 60 years” and “ \geq 61 years” based on their age recorded in IWRS. If age is missing in IWRS then age group is assigned based on the age derived from year of birth recorded in IWRS and date of first informed consent (age = year of date of first informed consent – year of birth).

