12.1 Subject Disposition

A summary of enrollment by region (Latin America vs Europe), country and site is provided for all randomized subjects. This summary is repeated on the OL Set.

The number and percentage of subjects who prematurely withdrew from treatment, prematurely withdrew from the trial before entering the OL phase, rolled over to the OL phase, prematurely withdrew from the trial during the OL phase and a breakdown of the corresponding reasons for treatment withdrawal and early trial discontinuation (summarized separately for blinded and OL phase) is provided.

The number and percentage of subjects randomized and treated is presented with the number and percentage of subjects included in each analysis set. Reasons for exclusion from each analysis set is not tabulated, but listed.

The number of subjects whose data is censored due to unblinding and/or AV application are provided for unblinding and/or AV use before dose 2 and after dose 2. The output is provided for the SAS and for all randomized subjects. A separate listing is provided indicating the date a subject was unblinded / received an AV. Subjects who have received an AV without being unblinded are also included in that listing.

The number and percentage of subjects who were not stratified correctly is presented along with the number of subjects who received an incorrect vaccine at first and/or second vaccination. The summary is done for all randomized subjects. These subjects are also listed.

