The analyses of the other secondary efficacy endpoint of COVID-19 cases in subjects 61 years or older are performed on the EAS, thereby restricting to subjects with age at trial entry ≥ 61 years. This analysis is not repeated by age group.

The analysis of the other secondary efficacy endpoint of BoD categories is performed on the EAS.

The analysis of the other secondary efficacy endpoint COVID-19 cases after first vaccination is performed on the SAS, restricted to subjects with a negative baseline serology (see Section 10.6.1).

All secondary efficacy endpoints mentioned in this section are provided for the interim analyses and for the primary efficacy delivery.

All applicable cases available in the respective data cut are used for the respective analyses.

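### SAP 10.7.6 and SAP 10.14 name different age sources for the same 18-60 and ≥61 groups, and the 10.14 fallback can only overstate age

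*SAP*

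**What the plan says.** SAP 10.7.6 lets adjudicated data overrule other data, with two exceptions. The first takes, for the by-age-group analysis of cases, "the age at trial entry as recorded on the CRF rather than the age at onset", the latter being the age the Adjudication Committee assesses.

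SAP 10.14 defines the groups 18 to 60 and ≥61 and assigns subjects to them "based on their age recorded in IWRS". It adds a fallback: "If age is missing in IWRS then age group is assigned based on the age derived from year of birth recorded in IWRS", computed as the year of first informed consent minus the year of birth.

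The analysis in older subjects (SAP 12.6.3.3) is run on the Efficacy Analysis Set (EAS), "restricting to subjects with age at trial entry ≥ 61 years". The matching estimand (SAP 9.5) refers to subjects ≥61 "years of age at randomization (complying with the definition of Efficacy Analysis Set) at least 15 days following second vaccination". Neither says whether that age comes from the CRF or IWRS.

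SAP 12.1 also plans a disposition table: "The number and percentage of subjects who were not stratified correctly is presented".

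**The concern.** The two rules point to different databases for the same classification, and no sentence ranks them. A programmer following 10.7.6 would use the CRF; one following 10.14 would use IWRS. For most subjects the answer is the same. For a subject entered as 60 in one system and 61 in the other, the age stratum depends on that choice.

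This matters because efficacy in subjects ≥61 is a named secondary objective (SAP 7.2.2). Efficacy summaries are repeated by age group (SAP 12.0), as are the Kaplan-Meier and Cox analyses (SAP 12.6.2.2). The older stratum has few cases, so one subject on the wrong side of the boundary shows in the estimate. Protocol 3.1.4 reports that the sponsor reassessed benefit and risk by age group, so these results were used.

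The fallback is a separate weakness. Subtracting calendar years is not age. Its error always goes upward, and at the 60/61 cut that means only into the older group. SAP 10.7.6 shows that an entry age exists on the CRF, so the approximation looks avoidable.

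**Working it through.** **Inputs.** 228 adjudicated cases, 21 of them in subjects over 60, and 25,062 subjects in the primary analysis (protocol 3.1.4). VE = 1 − [p/(1−p)]·(1/r), where p is the CVnCoV share of cases and r the follow-up ratio (SAP 12.6.2.1). With nv CVnCoV and np placebo cases this is VE = 1 − (nv/np)/r. Follow-up is summed over subjects (SAP 10.13).

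**The plan's own figure.** 21/228 = 9.2%, stated as 9%. That leaves 228 − 21 = 207 cases aged 18-60. As a cross-check, exact 95% intervals on 207 cases, with r set so that VE = 52.5%, match the reported 36.2-64.8% for splits of about 70/137 (r about 1.08) to 72/135 (r about 1.12). The counts are consistent.

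**One case leaving the ≥61 stratum.** The actual split and r in this stratum are not given. Assuming r = 1:

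| CVnCoV/placebo | VE | One CVnCoV case removed | One placebo case removed |
|---|---|---|---|
| 6/15 | 60.0% | 66.7% (+6.7) | 57.1% (−2.9) |
| 7/14 | 50.0% | 57.1% (+7.1) | 46.2% (−3.8) |
| 8/13 | 38.5% | 46.2% (+7.7) | 33.3% (−5.1) |
| 9/12 | 25.0% | 33.3% (+8.3) | 18.2% (−6.8) |
| 10/11 | 9.1% | 18.2% (+9.1) | 0.0% (−9.1) |
| 11/10 | −10.0% | 0.0% (+10.0) | −22.2% (−12.2) |

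The shift runs from 2.9 to 12.2 points. It scales with 1/r, so over r = 0.9 to 1.2 the range is 2.9/1.2 = 2.4 to 12.2/0.9 = 13.6 points.

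**Displaced person-time only.** Assume that 9% to 25% of 25,062 subjects are ≥61, that is 2,256 to 6,266, or about 1,128 to 3,133 per arm. One subject is then 1/1,128 = 0.09% to 1/3,133 = 0.03% of an arm's follow-up. For VE between 0 and 50% that is under 0.1 point.

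**Scale against sampling error.** At 9/12 and r = 1 the exact 95% interval for VE is −93.9% to 72.1%.

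**Fallback.** Calendar-year subtraction equals true age if the birthday has passed by the consent date, and true age plus one if it has not. Someone born in December 1960 who consents in April 2021 is 60, but 2021 − 1960 = 61 puts that person in the older group. No birth date gives an error the other way.

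**The case against.** Exception 1 in SAP 10.7.6 was written to prefer entry age over adjudicated age at onset, not CRF over IWRS. The SAP change history shows that the age-group derivation was added in version 4.0, before the final efficacy analysis, so one can read the two together as entry age, derived as in 10.14. That explains the conflict but does not remove it: 10.7.6 still says CRF, and no edit to it is logged with that addition.

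A reader might infer that the SAP would count a subject's case in one age stratum and the follow-up in the other. The documents do not support that. SAP 12.6.3.3 restricts subjects and SAP 10.13 sums follow-up subject by subject, so one set most naturally supplies both.

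A reader might also take the table of incorrectly stratified subjects as evidence that age discordance is expected. Stratification is by country as well as age, so the table shows only that stratification errors in general are tracked.

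The fallback invites a large figure. For consent on 9 April, 266 of 365 birthdays (73%) are still to come, so that share of true 60-year-olds would be misclassed. This is conditional on the fallback being used on that date. Protocol 7.3.1 has demographics entered before assignment, with age as a stratification factor, so missing IWRS ages should be rare. It is not an expected effect.

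Finally, the ≥61 endpoint has no confirmatory testing (SAP 12.6.3.3), and its interval is far wider than the shift from one case. Both points stand and limit the consequence.

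**Conclusion.** The point holds as a conflict of stated sources plus a one-directional fallback. For any subject whose CRF and IWRS ages straddle 60/61, the SAP does not determine the stratum. If one such subject is a case, its removal from the ≥61 group moves VE by about 3 to 12 points, given 21 cases, r = 1 and splits from 6/15 to 11/10. The size comes from the case changing stratum; the person-time effect is negligible. The documents give neither the number of discordant subjects nor the number with a missing IWRS age, and either may be zero. The overall primary result, the sample size and alpha are unaffected. The correction is worth making because the rules as written conflict or misclassify and the repair is cheap.

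**What to change.** - Name one age-at-entry variable in SAP 10.7.6, 10.14 and 12.6.3.3, and use it for both cases and follow-up in every by-age efficacy analysis.
- Replace the year-subtraction fallback with the age at trial entry recorded on the CRF.
- Keep the IWRS stratum only where the randomisation stratum is meant, as in the Cox adjustment.
- Report how many subjects have IWRS and CRF ages in different groups.
- SAP 6.1 states that version 5.0 was written by an unblinded team, and SAP 12.6.1 allows some primary and key secondary efficacy outputs to be re-run because of site AR009. If any by-age efficacy output is re-run, show it under the other age source as a sensitivity analysis, so that the choice made after unblinding is visible.

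The cost is a wording change, one derived variable and one count. By-age tables may shift by a few subjects.

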10.8 Definition of Asymptomatic Cases of SARS-CoV-2 Infection and Onset Date

In this trial no active surveillance for asymptomatic SARS-CoV-2 infections is foreseen. Subjects are reminded to contact the trial site immediately if he/she had a positive SARS-CoV-2 test performed outside of the trial site, whether or not they were symptomatic (COVID-19 illness) or asymptomatic at the time of the test.

If the subject was asymptomatic, trial staff contacts the subject immediately to collect information about the positive SARS-CoV-2 test the subject reported. The subject should be retested as soon as feasible to confirm the result. A positive RT-PCR test result is considered definitive as a virologically-confirmed case of SARS-CoV-2 infection.

If the subject is confirmed to have SARS-CoV-2 infection, the subject is followed by trial staff for at least 2 weeks for the development of any COVID-19 symptoms, to ensure that this is an asymptomatic infection. If the subject develops COVID-19, he/she is followed up as a COVID-19 case. If the subject is confirmed to be an asymptomatic infection, information is collected by the trial staff and documented on the appropriate CRF page.

The onset date of an asymptomatic infection is defined as the date of the positive RT-PCR test result performed by a central laboratory.

Scenario A: Asymptomatic cases are not collected in the OL Phase.

10.9 Burden of Disease

Two different BoD scores are calculated for each subject, based on their first episode of virologically confirmed COVID-19 case meeting the case definition for primary efficacy analysis.

BoD Score #1 is assigned as follows (considering only first episodes):

- No disease (i.e. not infected or only asymptomatic infection): Score = 0
- Mild or moderate disease (as defined in Section 10.7.3): Score = 1
- Severe disease (as defined in Section 10.7.3): Score = 2

BoD Score #2 is assigned as follows (considering only first episodes):

- No disease (i.e. not infected or only asymptomatic infection): Score = 0
- Disease without hospitalization: Score = 1
- Disease with hospitalization: Score = 2
- Death: Score = 3.

10.10 Individual and Site-Level Unblinding Date

Although some members of the combined Sponsor and CRO study team were unblinded before EOT (e.g. the full CRO study team and selected members of the Sponsor study team were unblinded at the time of the primary efficacy analysis delivery), study subjects and site personnel were originally supposed to remain blinded until EOT.

Transition from the randomized observer-blinded phase to the open-label phase and related unblinding procedures of study subjects and site personnel before EOT are conducted on country/site level and start immediately after full competent authority and Ethics Committee approval of Protocol version 4.0 in the respective country/site. This is referred to as site-level unblinding. If subjects were individually unblinded before site-level unblinding this is referred to as individual unblinding.

Unblinding date (individual unblinding): The date and time stamp created by the IWRS system when the site entered the individual unblinding request.

Unblinding date (site-level unblinding): The date and time created by a preconceived script run by the IWRS provider on the IWRS system. This date and time are the date and time that the script is run by the designated person from the CRO. In case the IWRS data does not provide one consolidated unblinding date as described in Table 8, the below logic is implemented in CDISC.

Table 8: Logic Behind the Unblinding Date in IWRS

Individual Unblinding Date is	Site Unblinding Date is	IWRS Unblinding Date Shows
None	Not before EOT	Empty
Available	Not before EOT	Individual unblinding date
None	Before EOT	Site Unblinding Date
Available	Before EOT	Min(Individual unblinding date; Site Unblinding Date)

10.11 Censoring Rules for Subjects Unblinded and/or Treated with Authorized/Licensed Vaccine for Preventing COVID-19

The following was decided based on ethical reasons and requests from health authorities and applies to the blinded study phase already: If during the conduct of study CV-NCOV-004 an AV becomes available to subjects, these subjects can request to be individually unblinded from the study treatment to decide whether they would like to receive the AV. The following censoring rules are applied to these subjects to avoid any study bias. Further inclusion/exclusion rules are specified in the relevant analysis populations (See Section 0).

- If the case start day and the unblinding day occur on the same day the case counts for the analysis. (Censoring starts at the day after the unblinding.)

The following details are to be followed regarding censoring the day after receiving the AV:

- Times are not relevant as neither AV time nor case start time are collected.
- If AV date is complete then censoring starts at first day after the AV day.
- If AV date is incomplete (only day missing) then censoring starts after this month.
- If AV date is incomplete (month missing, year available) then censoring starts after this year.
- If AV date is completely missing then no censoring can be made.

As these imputations of incomplete AV dates are not an ideal solution this is only to be considered as a fallback solution in case complete AV dates cannot be retrieved and as an interim workaround for unclean data during study conduct.

All incomplete or missing AV dates need to be queried.

Site level unblinding:

As each of these subjects receives an unblinding date and time that feeds into the analysis data exactly like the individual unblinding date and time, no difference in censoring process needs to be made for these subjects.

If the subject has never received a CVnCoV dose in this study the subject is discontinued after site-level unblinding, so only the related EOT assessments are censored if performed after the day of unblinding. (Provided the subject has not received an AV before unblinding. In that case the above rules for individual unblinding with AV receipt also apply.)

If the subject has received at least 1 dose of CVnCoV in this study the subject is not automatically discontinued and the subject's data is censored as specified above for individually unblinded subjects.

10.12 Unblinding of Site AR009

Due to accidental unblinding at Site AR009 between 09 April 2021 and 16 Apr 2021 the following unblinding dates are created in CDISC:

Table 10 Unblinding Date for Subjects from Site AR009

Subject Randomization Date	Unblinding Date in IWRS Database	Consequence on Unblinding Date
Before or on 09-Apr-2021	None	Set to 09-Apr-2021
	Before 09-Apr-2021 (incl.)	Leave as is
	After 09-Apr-2021	Set to 09-Apr-2021
After 09-Apr-2021 and until 16-Apr-2021 (inclusively)	None	Set to randomization date
	Before 16-Apr-2021 (incl.)	Set to randomization date
	After 16-Apr-2021	Set to randomization date
After 16-Apr-2021	None	Leave as is
	Before 16-Apr-2021 (incl.)	N/A
	After 16-Apr-2021	Leave as is

10.13 Event Dates, Follow-Up Time, Time to Event Calculation and Censoring

Subject's follow-up time and rules for time to event calculations and censoring are dependent on the definition of the endpoint analyzed.

General formulae for the calculation of follow-up time and time to event are provided below. Table 11 further summarizes the definitions and derivations for the dates to be included in the respective formulae based on the endpoint analyzed.

- For each subject, the follow-up time (days) is defined as:

$$\text{Follow Up Time (days)} = \text{End date of Follow Up} - \text{Start date of Follow Up} + 1.$$

- For each event type, the total follow-up time within each vaccine group is calculated as the sum of all single follow-up times in that group. The total follow-up (years) is calculated as

$$\text{Total Follow Up Time (years)} = \frac{\text{Total Follow Up time (days)}}{365.25}$$

- The time to event (days) for both subjects with an event and censored subjects is calculated as follows:

$$\text{Time to Event (days)} = \text{Event/Censoring Date} - \text{Start Date} + 1.$$

Table 11: Event Dates, Censoring and Follow-Up Time Calculation

ENDPOINT SHORT DESCRIPTION	START DATE	EVENT DATE*	CENSORING DATE#	END DATE OF FOLLOW-UP
FIRST EPISODES OF COVID-19 CASES⁺	2 nd vac. + 15 days	Date of symptoms onset	Min (unblinding date + 1; date AV + 1; trial termination date; cut- off date [^])	Min (Event date; Censoring date; 18-Jun-2021 [§])
FIRST EPISODES OF MODERATE TO SEVERE COVID-19 CASES	2 nd vac. + 15 days	Date of symptoms onset	Min (first episode of mild COVID-19 case date; unblinding date + 1; date AV + 1; trial termination date; cut- off date [^])	Min (Event date; Censoring date; 18-Jun-2021)
FIRST EPISODES OF SEVERE COVID-19 CASES	2 nd vac. + 15 days	Date of symptoms onset	Min (first episode of mild or moderate COVID-19 case date; unblinding date + 1; date AV + 1; trial termination date; cut- off date [^])	Min (Event date; Censoring date; 18-Jun-2021)
FIRST EPISODES OF COVID-19 CASES IN SUBJECTS ≥ 61 YEARS OF AGE	2 nd vac. + 15 days	Date of symptoms onset	Min (unblinding date + 1; date AV + 1; trial termination date; cut- off date [^])	Min (Event date; Censoring date; 18-Jun-2021)
BURDEN OF DISEASE SCORES	2 nd vac. + 15 days	Date of symptom onset of corresponding COVID-19 case	Min (unblinding date + 1; date AV + 1; trial termination date; cut- off date [^])	Min (Event date; Censoring date; 18-Jun-2021)
FIRST EPISODES OF MILD COVID- 19 CASES	2 nd vac. + 15 days	Date of symptoms onset	Min (first episode of moderate or severe COVID-19 case date; unblinding date + 1; date AV + 1; trial termination date; cut- off date [^])	Min (Event date; Censoring date; 18-Jun-2021)

ENDPOINT SHORT DESCRIPTION	START DATE	EVENT DATE*	CENSORING DATE#	END DATE OF FOLLOW-UP
FIRST EPISODES OF MODERATE COVID-19 CASES	2 nd vac. + 15 days	Date of symptoms onset	Min (first episode of mild or severe COVID- 19 case date; unblinding date + 1; date AV + 1; trial termination date; cut- off date [^])	Min (Event date; Censoring date; 18-Jun-2021)
FIRST EPISODES COVID-19 CASES WITH SYMPTOM ONSET AT ANY TIME AFTER THE FIRST TRIAL VACCINATION⁺	1 st vac.	Date of symptoms onset	Min (unblinding date + 1; date AV + 1; trial termination date; cut- off date [^])	Min (Event date; Censoring date; 18-Jun-2021)

VAC = VACCINATION
+ FOR ENDPOINTS ASSESSED IN NAÏVE SUBJECTS AS WELL AS ENDPOINT ASSESSED IN SUBJECTS REGARDLESS OF THEIR BASELINE SEROLOGY STATUS
